## 5. STATISTICAL METHODS

For continuous variables, at the reported visits or in overall summary, descriptive statistics will consist of: number of non-missing observations (n), mean, median, standard deviation (SD), minimum, and maximum. It is to be noted that number of participants with observations could include participants with data that were observed as well as those that were imputed for specific types of missing data or determined based on handling of intercurrent events, as explained in later sections.

For categorical variables, frequencies and percentages will be displayed for each category.

In the context of efficacy-related tables, percentages will be calculated based on the denominator of number of participants with data depending on the handling of intercurrent events as well as imputations of missing data as explained in the later sections. For non-efficacy tables, percentages will be calculated based on the corresponding analysis population unless otherwise specified in the mock shell.

Listed below are some subgroups for potential exploratory subgroup analysis:

- Race (Black/African American vs. Non-Black/Non-African American)
- Age group (<30 years old vs.  $\geq 30$  years old)
- SALT Score at baseline (50 to <75, 75 to <95, 95 to 100)
- Age at disease onset ( $\leq 12$  years old vs.  $> 12$  years old)
- Presence of autoimmune comorbidities (Yes vs. No)
- Presence of atopic comorbidities (Yes vs. No)
- Duration of current episode (< 2 years vs.  $\geq 2$  years)
- Baseline elevated IgE (Yes vs. No)

### 5.1 Demographics and Baseline Characteristics

Demographics and baseline characteristics will be summarized by treatment groups based on safety analysis set. Listing of demographics and baseline characteristics will be presented.

### 5.2 Medical and Disease History

Non-alopecia medical history and comorbid (concomitant) non-alopecia medical illness will be summarized by primary system organ class (SOC) and preferred term (PT) for each treatment group. Alopecia disease history and comorbid (concomitant) alopecia medical illness will be summarized separately in the safety analysis set by current scalp AA subtype and treatment group. The table will be sorted by decreasing frequency of SOC followed by PT (or

scalp AA subtype in case of alopecia disease history) based on the overall incidence across treatment groups.

Medical history will be listed by SOC and PT, sorted by treatment groups based on the safety analysis set.

### **5.3 Prior and Concomitant Medications/Procedures and Prohibited Medications**

Below summaries will be provided on prior and concomitant medications/procedures for the safety analysis set, sorted by decreasing frequency of ATC level 2 and preferred term, based on the overall incidence for the combined IMG-007 treatment group.

- Summary of prior alopecia medications by ATC level 2 term and preferred term.
- Summary of prior alopecia medications by reason for discontinuation, ATC level 2, and preferred term.
- Summary of prior non-alopelia medications ATC level 2 term and preferred term.
- Summary of concomitant medications by ATC level 2 term and preferred term.

Listings will be provided for prohibited medications, prior alopecia and non-alopelia medications/procedures, and concomitant medications by treatment for the safety analysis set. The listings will include reported term, ATC level 2, preferred term, Indication, dose, frequency, route, start date, study day onset (for medications started before treatment, the study day onset (defined as date of medication start - date of the first dose; for medications started on or after treatment, the study day onset = date of medication start - date of the first dose+1), the study end date (defined similarly as for study onset day).

### **5.4 Prior and Concomitant Non-Drug Therapies and Procedures**

Below summaries will be provided on prior and concomitant non-drug therapies/ procedures for the safety analysis set.

- Summary of prior non-drug therapies/procedures related to AA by SOC and PT.
- Summary of prior non-drug therapies by SOC and PT for treating conditions other than AA.
- Summary of concomitant non-drug therapies by SOC and PT.

A listing will be provided for non-drug therapies and procedures. The listing will include reported term, dictionary terms, Indication, start date, study day onset (defined similarly as for medications in above section), end date and end study day (defined similarly as for medications in above section).

## 5.5 Participant Disposition

Summaries will be provided for the following data in each treatment group for the full study sample (i.e., all screened participants who signed informed consent):

- The number and percentage of participants screened, and who failed screening, along with the reasons for screen failure. (This will be reported only in the overall group.)
- The number and percentage of participants included in each treatment group as well as in each study analysis set.
- The number and percentage of participants who completed the 4-week dosing period, discontinued the 4-week dosing period with the reason for discontinuation, completed the 16-week treatment period, discontinued 16-week treatment period with reason for discontinuation, completed the study, and discontinued the study with reason for discontinuation, consented for the extended follow-up, completed the extended follow-up, and discontinued the extended follow-up with reason for discontinuation.

A summary will be provided for major protocol deviations by deviation category and treatment group for the safety analysis set. The protocol deviations flagged as ‘CSR Reportable’ will be classified as major protocol deviations.

The following listings will be provided.

- The participant disposition listing comprises various details, including the date of informed consent form (ICF) signing, ICF and protocol versions, enrolment or screen failure dates, and the completion/discontinuation date of the 4-week dosing period, date of 16-week treatment period/discontinuation, reason for discontinuation, study completion status, date of study completion, among other factors.
- A listing of screen failures with inclusion criteria not met and/or exclusion criteria met.
- Listing of protocol deviation.

## 5.6 Treatment Exposure and Compliance

A descriptive summary of treatment exposure will be provided on safety analysis set for the following data.

- summary of dose administered (in mg) by treatment and visit
- summary for dose-weight proportion with the categories; < 3 mg/kg, 3-6 mg/kg, >6-9 mg/kg, and >9 mg/kg.
- Number and percentage the participants with infusion frequency (1, 2 and 3 infusions).
- Summary on overall duration of the treatment.

Overall duration of each treatment will be provided irrespective of intermittent dose interruptions. The duration of treatment exposure in the study is calculated in days as:

$$(\text{Date of last dose of IMP} - \text{date of first dose of IMP}) + 84$$

Categorical summary of visit wise treatment compliance showing the number (n) and percentage of participants falling within the following ranges: <80%, 80%-<100%, 100%-

120%, >120% will be presented for each treatment. The compliance with protocol-defined investigational product will be calculated as follows: Treatment Compliance= (actual total dose administered) / (total planned dose) x 100%.

A listing of treatment exposure will be provided on safety analysis set, which includes start and date/time of infusion, infusion administered arm, dose, infusion rate, dose interruption, and details of dose interruption.

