The extended follow-up period after EOS consists of two visits: Week 30 (Day 211) and Week 36 (Day 253).

The schedule of assessments (SoA) at each visit is summarized in [Table 1](#). Assessments of efficacy, safety will be conducted throughout this study (until extended follow-up period post EOS) and PK, PD, and immunogenicity data will be collected until the end of EOS visit.

Participants who discontinue treatment early (before completing the 4-week dosing period) should continue with all the remaining study visits.

Participants who withdraw from the study any time before the Week 16 visit should complete the Week 16 (Day 113)/EOT visit at withdrawal.

Participants who withdraw from study early during the follow-up period should complete the Week 24 (Day 169)/EOS visit at withdrawal.

Participants who discontinue early after the Week 24/EOS visit but before the Week 36 visit should complete Week 36 (Day 253) visit at withdrawal.

A participant who withdraws from the study prior to receiving two doses of study treatment (i.e., completing the Week 2 visit) for reasons other than AEs will be replaced.

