### **Treatment Period:** Day 1 (Baseline) to Day 113 (16 weeks)

Participants who meet all eligibility criteria will be enrolled and will receive three IV infusions of IMG-007 [REDACTED] or [REDACTED] administered 2 weeks apart at the Baseline (Day 1), Week 2 (Day 15), and Week 4 (Day 29) visits. The study site will contact participants by telephone approximately 24 hours after each infusion for assessment of AEs and/or concomitant medications.

On dosing days, study treatment will be administered as an IV infusion over approximately 60 minutes with a slower rate during the first 15 minutes. Participants will be closely monitored at the study site for a minimum of 1 hour after completion of each infusion or until any AEs observed during the observation have resolved or stabilized, whichever is longer. For diagnostic purposes, any participant who experiences any systemic infusion-related event should have a blood sample taken ideally 30–60 minutes after the onset for tryptase testing, and samples should be analyzed by a local laboratory if feasible. Study sites should have access to equipment or facilities for the management of potential hypersensitivity reactions.

Beyond dosing visits, participants will complete visits at Week 1 (Day 8), Week 6 (Day 43), Week 8 (Day 57), Week 12 (Day 85) and Week 16 (Day 113)/end of treatment (EOT).

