#### 3.1 Safety analysis set

The safety analysis set includes all participants who received at least one dose of study treatment.

Safety analysis set will be used for analyses demographic and baseline characteristics, and safety data.

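### SAP 5.6 counts 84 days after the last infusion as exposure in the study with no cap at study exit, so anyone who leaves the study or dies sooner is over-credited

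*SAP*

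**What the plan says.** SAP 5.6 (Treatment Exposure and Compliance) includes overall treatment duration in the exposure summary. The formula is introduced by "The duration of treatment exposure in the study is calculated in days as" and is the date of last dose minus the date of first dose, plus 84. Its only qualifier is "Overall duration of each treatment will be provided irrespective of intermittent dose interruptions". Withdrawal, last contact and death are not mentioned there, and no cap appears elsewhere in the text available.

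The summary is on the safety analysis set, and SAP 3.1 says "The safety analysis set includes all participants who received at least one dose of study treatment". One infusion is enough.

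Protocol 4.1.2 foresees early departure from the study: "Participants who withdraw from the study any time before the Week 16 visit should complete the Week 16 (Day 113)/EOT visit at withdrawal". It also provides that a participant who withdraws "prior to receiving two doses of study treatment (i.e., completing the Week 2 visit) for reasons other than AEs will be replaced". Protocol 6.10.2 lists withdrawal of consent, loss to follow-up and death among the reasons for leaving.

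Two other SAP sections bear on the point. SAP 5.8.1 closes the TEAE windows at the Week 24 or Week 36 visit, or at end of study if that is earlier. SAP 5.5 tabulates discontinuation of the dosing period, the treatment period and the study, and lists completion and discontinuation dates.

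**The concern.** The label says the quantity is exposure in the study, but the formula uses dose dates only. It agrees with time in the study only if the participant stayed at least 84 days after the last infusion. For anyone who left sooner, the table counts days after departure, and after a death it would count days after death.

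The two safety displays also run on different clocks for the same person: the TEAE window stops at study exit and the exposure duration does not. A reader uses the exposure table to judge how much experience lies behind the safety results. The error always runs upward, and it is largest for those who left soonest after an infusion. In a cohort of six, one such person moves the mean visibly.

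**Working it through.** **Inputs**
- Dosing: three infusions "administered 2 weeks apart at the Baseline (Day 1), Week 2 (Day 15), and Week 4 (Day 29) visits" (SAP 2.3).
- Treatment period: Day 1 to Day 113, which is 113 - 1 = 112 elapsed days (SAP 2.3).
- Add-on: 84 days (SAP 5.6). It equals 113 - 29, the interval from the Week 4 dose to Week 16. Protocol 2.5.1 describes Week 16 as 12 weeks after the last dose.
- Cohort sizes: 6 and 24 (SAP 2.1).
- Number and timing of early leavers: not in the documents. The cases below are assumptions.

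**The plan's own figure.** On-schedule completer: (29 - 1) + 84 = 112 days. This matches the treatment period, so the formula itself is not miscalculated. It also shows that the SAP counts elapsed days, with no added 1.

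**Comparison**
- As written: (last dose day - first dose day) + 84.
- Capped: min(last dose day + 84, exit day) - first dose day.
- Excess: 84 - (exit day - last dose day) if positive, otherwise 0. The maximum is 84, for exit on the day of the last infusion.

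| Case | As written | Capped | Excess |
|---|---|---|---|
| 1 dose, exit Day 10 | 0 + 84 = 84 | 10 - 1 = 9 | 75 |
| 2 doses, exit Day 15 | 14 + 84 = 98 | 15 - 1 = 14 | 84 |
| 2 doses, exit Day 20 | 14 + 84 = 98 | 20 - 1 = 19 | 79 |
| 3 doses, exit Day 43 | 28 + 84 = 112 | 43 - 1 = 42 | 70 |
| 3 doses, exit Day 85 | 112 | 85 - 1 = 84 | 28 |
| 3 doses, exit Day 113 or later | 112 | 112 | 0 |
| 1 dose, followed to Day 169 | 84 | 84 | 0 |
| 2 doses, followed to Day 169 | 98 | 98 | 0 |

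The last two rows are participants who stop dosing but stay in the study. They are unaffected.

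**Effect of one leaver on the mean.** A participant who withdraws before the second dose for a reason other than an AE is replaced but stays in the safety set, so the denominators become 7 and 25. Otherwise they are 6 and 24.
- 1 dose, exit Day 10. Not replaced: 75/6 = 12.5 and 75/24 = 3.1 days. Replaced: 75/7 = 10.7 and 75/25 = 3.0 days.
- 2 doses, exit Day 20: 79/6 = 13.2 and 79/24 = 3.3 days.
- 3 doses, exit Day 43: 70/6 = 11.7 and 70/24 = 2.9 days.

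**The case against.** The best defence is that this is a drug-exposure variable and was never meant to measure follow-up. Protocol 2.5.1 expects a reasonable level of systemic exposure by Week 16, 12 weeks after the last dose, and leaving the study does not remove infused antibody. The formula does not match AE observation for completers either: they are followed to Day 253 and credited with 112 days. The summary is descriptive, the number of infusions is tabulated beside it, and SAP 5.5 reports who left, when and why.

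Much of this stands. A fixed tail is defensible, and the 84 days are not the fault. But the SAP gives no such rationale and labels the result as exposure in the study, which is untrue for an early leaver. No summary of observed follow-up time is planned that would let a reader correct the mean directly.

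Some stronger readings are tempting but not supported:
- *The TEAE results are biased.* They are numbers and percentages of participants (SAP 5.8.1, Protocol 11.3.1), and no person-time rate is planned.
- *Everyone who stops treatment early is over-credited.* Protocol 4.1.2 has them continue with the remaining visits, and those who stay 84 days after the last dose are credited correctly.
- *The missing cap is why a one-infusion participant shows 84/112 = 75% of full-course duration.* That follows from the fixed tail, and the cap leaves it unchanged for someone who stays in the study.
- *Nothing could be reported after exit.* Protocol 8.2.1 still allows treatment-related SAEs to be reported to the sponsor after the follow-up period.

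**Conclusion.** The point holds, at low materiality. As written, SAP 5.6 overstates exposure in the study by 84 minus the days followed after the last infusion, up to 84 days, for anyone who leaves the study or dies within that interval. Under the assumed cases, one leaver shifts the mean by roughly 11 to 13 days in Cohort 1 and about 3 days in Cohort 2. If nobody leaves that early, the effect is zero. It is a gap in the definition, confined to one descriptive summary, and no TEAE or efficacy result depends on it. It would matter more if exposure-adjusted rates were later built on this variable.

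**What to change.** In SAP 5.6, define duration as the earliest of (date of last dose + 84 days, date of study discontinuation, date of last contact, date of death) minus the date of first dose. Use elapsed days throughout, with no added 1 in any term, so that an on-schedule completer still shows 112 days.

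The cost is one line in the SAP and a small program change. SAP 5.5 already lists discontinuation dates, and Protocol 8.1.3 collects date of death. The only downside is a slightly smaller mean exposure if anyone leaves early. If the sponsor prefers the fixed tail as a pharmacological window, the alternative is to label it as nominal and report observed follow-up time beside it.

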## 5.7 Analysis of Efficacy Variables

All the efficacy evaluations will be performed on modified full analysis set unless otherwise specified.

### 5.7.1 Analysis of Secondary Efficacy Variable

A descriptive summary (n, mean, median, standard deviation, minimum, maximum, Q1, Q3, standard error) will be provided for percentage change from baseline in SALT score at Week 24 by treatment.

A mixed model repeated measure (MMRM) analysis will be performed for percentage change from baseline in SALT score over time up to Week 24 by considering treatment, visits (up to week 24), and treatment-visit interaction as fixed effects, along with baseline SALT score as a covariate; unstructured covariance matrix will be used for the model errors (Alternative covariance matrices such as Compound symmetry will be used if the unstructured covariance matrix fails to converge) and Kenward-Roger (KR) approximation is used to estimate denominator degrees of freedom.

MMRM will compare the effect of each IMG-007 doses at each post baseline visit versus the baseline based on difference relative to zero. Least square means and their corresponding 95% confidence intervals will be provided for each treatment along with the p-value at nominal two-sided 5% significance level.

In case of convergence issue occurred for the MMRM model, analysis of covariance (ANCOVA) will be used to compare the effect of IMG-007 with the same factors and covariate considered for MMRM. Least square means and their corresponding 95% confidence intervals will be provided at each visit.

Based on the estimand framework introduced in [ICH E9\(R1\)](#) additional details relating to the definition of the estimand is proposed.

Line graphs will be generated to illustrate the percentage change from baseline in the total SALT scores. The X-axis will represent visit, while the Y-axis will denote the change from baseline or percentage change from baseline.

### 5.7.2 Analysis of Key Exploratory Efficacy Variables

#### 5.7.2.1 *Continuous efficacy endpoints*

All continuous exploratory efficacy endpoints will be analyzed using the same approach as that used for the main analysis of percentage change in SALT from baseline to Week 24.

For the timepoints beyond Week 24, separate MMRM models will be developed to include all the post-baseline visits until Week 36. However, the estimates and p-values will be reported only for the timepoints beyond Week 24 from these models. The results of earlier timepoints will be reported from the models up to Week 24.

ANCOVA will be utilized as explained in the main analysis section if the MMRM model fails to converge.

#### Sensitivity analysis

Sensitivity analysis that are specified for the secondary endpoint will be repeated for the key continuous exploratory endpoints as well. For the timepoints beyond Week 24, a separate MMRM model will be developed to include all the post-baseline visits until Week 36. However, the estimates and p-values will be reported only for the timepoints beyond Week 24 from these models. The results of earlier timepoints will be reported from the model up to Week 24.

#### 5.7.2.2 *Responder type (binary) efficacy endpoints*

The responder type (binary) endpoints will be reported using frequency and percentage by treatment along with the 95% Clopper-Pearson exact confidence interval for the proportion.

Based on the estimand framework introduced in [ICH E9\(R1\)](#), additional details relating to the definition of the estimand is proposed.

Handling of intercurrent events (for responder type binary endpoints) of treatment discontinuation and prohibited medication:

- *Treatment discontinuation*: Treatment policy strategy will be followed. i.e., all the collected data available after treatment discontinuation will be included in the analysis.
- *Any prohibited medication*: Participant will be reported as non-responder at all the visits occurring after the prohibited medication start.

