Efficacy Analyses

Continuous efficacy variables will be summarized using descriptive statistics which will include mean, median, minimum, maximum, Q1 and Q3, and standard deviation. Categorical efficacy variables will be summarized by

frequency and percentage for each category. Analysis will be presented by cohort (dose group) as well as the overall population (two cohorts pooled) if efficacy results across various endpoints by dose group are similar. In general, efficacy analyses will be descriptive based on observed data. For the key efficacy endpoints based on SALT score, besides the descriptive analyses, additional analyses will be planned, including mixed model repeated measure (MMRM) analysis and one sample t-test for percent (%) changes and absolute changes from baseline in SALT over time (by visit) up to Week 24 by dose group and in the pooled population (if efficacy results across various efficacy endpoints by dose group are similar), to evaluate if these changes are nominally significant. Various imputation methods will also be explored in addition to the observed value method. Treatment policy-based estimand will be used for all efficacy analysis. Further details including handling of specific intercurrent events and other imputation methods will be specified in the prospective statistical analysis plan (SAP).

PK Analyses

Serum concentration data will be tabulated and summarized (geometric mean, arithmetic mean, minimum, maximum, SD and % coefficient of variation) by treatment group for each visit at which samples were taken.

Immunogenicity Analyses

The immunogenicity results will be summarized using descriptive statistics by the number and percentage of participants who develop detectable ADA. The incidence of positive ADA will be reported for evaluable participants. The effect of immunogenicity on PK, efficacy and safety may be evaluated if data allows.

PD Analyses

Biomarker data will be listed by participant and visit/timepoint.

Timing of analyses

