## 1. OVERVIEW

The purpose of the statistical analysis plan (SAP) is to ensure the credibility of the study results by pre-specifying statistical approaches for the analysis of this study. The SAP is intended to be a comprehensive and detailed description of strategy and statistical techniques to be used to realize the analysis of data for IMG-007-202. This SAP was written and finalized prior to the database lock, based on study protocol IMG-007-202 version 4 and 4.1(Canada only) (02 August 2024). Any methodological deviations from the protocol are documented. The analyses laid out in this SAP will be implemented by MeDaStats LLC for Inmagene Biopharmaceuticals.

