### Sensitivity analysis

No prespecified sensitivity analyses will be performed. Additional post-hoc sensitivity analysis will be considered as appropriate later.

Line plots will be included to depict responder-type of endpoints of SALT for each treatment group. The X-axis will feature visits, and the Y-axis will represent the proportion of participants, expressed as a percentage.

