### **5.7.3 Analysis of Other Exploratory Efficacy Variables**

All the continuous exploratory variables will be analyzed using descriptive statistics (n, mean, median, standard deviation, minimum, and maximum).

All the binary exploratory variables will be summarized with frequency and percentages.

Intercurrent events will be handled as described in section [5.7.1](#) and [5.7.2.2](#) based on the characteristics of the analysis variable. No additional missing data imputations and sensitivity analysis are applicable for other exploratory endpoints.

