## 5.10 Analysis of Pharmacodynamic Data

### 5.10.1 Handling of PD data based on the prohibited medication use

All the PD assessments (except OX40 occupancy on CD4+ T cell and OX40+/CD4+ T cell in CD4+ T cell) will be treated similar to the secondary efficacy assessment for handling the intercurrent event (prohibited medication). That is, all PD assessments after the start date of first prohibited medication use of each participant will be set to missing. The results for OX40 occupancy on CD4+ T cells and OX40+/CD4+ T cells within CD4+ T cells will be used as collected.

Statistical analysis of the following pharmacodynamic variables will be presented.

- Listing of RO (%) by visit for individual
- Table and figure of RO (%) over time for each dose group
- Listing of Percentage of OX40+/CD4+ T cell in CD4+ T cell (%) by visit for individual
- Table and figure of Percentage of OX40+/CD4+ T cell in CD4+ T cell over time for each dose group
- Listing of Olink target 48 cytokine panel proteins levels in serum (pg/mL), by visit for individual (45 proteins)
- Table and figure of Olink target 48 cytokine panel proteins levels in serum (pg/mL) log10 transformed change from baseline over time for each dose group (45 proteins)
- Listing of Olink target 48 immune surveillance panel proteins levels in serum (pg/mL), by visit for individual (44 proteins)
- Table and figure of Olink target 48 immune surveillance panel proteins levels in serum (pg/mL) log10 transformed change from baseline over time for each dose group (44 proteins)
- Figure of baseline Th1/Th2/Th17/Th22 fold change vs healthy subject for individual
- Figure of baseline, Week 16 and Week 24 Th1/Th2/Th17/Th22 fold change vs healthy subject for each dose group
- Table and figure of IgE (IU/mL) log10 transformed change from baseline over time for each dose group
- Listing of levels of IgE for individual
- Listing of OX40 positive cells (cells/mm^2) in biopsy by visit for individual
- Table and figure of Week 24 LS (Lesion) vs Week 16 LS vs baseline LS vs baseline NL (non-lesion) OX40 positive cells in biopsy for each dose group
- Listing of OX40L positive cells (cells/mm^2) in biopsy by visit for individual
- Table and figure of Week 24 LS vs Week 16 LS vs baseline LS vs baseline NL OX40L positive cells in biopsy for each dose group
- Listing of Tryptase positive cells (cells/mm^2) in biopsy by visit for individual

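### The protocol names treatment policy for all efficacy analysis, but the SAP counts binary endpoints as non-response after any prohibited medication, and no readable SAP summary gives the treatment-policy SALT30 rate

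*SAP*

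**What the plan says.** **Protocol.** The synopsis (1.1, Efficacy Analyses) states: "Treatment policy-based estimand will be used for all efficacy analysis". Its next sentence leaves the handling of specific intercurrent events to the SAP. Protocol 11.3.3 does not repeat the estimand statement; it says that efficacy analyses are in general descriptive and use observed data.

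**SAP, binary endpoints.** Section 5.7.2.2 follows treatment policy after treatment discontinuation. After any prohibited medication the rule is: "Participant will be reported as non-responder at all the visits occurring after the prohibited medication start". On sensitivity analysis for these endpoints it says "No prespecified sensitivity analyses will be performed", leaving post-hoc work open. For the other exploratory endpoints, section 5.7.3 says "Intercurrent events will be handled as described in section" 5.7.1 and 5.7.2.2.

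**SAP, continuous endpoints.** The intercurrent-event text of 5.7.1 cannot be read in the public copy. There is an indirect pointer in 5.10.1. It says that pharmacodynamic data, apart from two OX40 measures, are treated in the same way as the secondary efficacy assessment, and then that "all PD assessments after the start date of first prohibited medication use of each participant will be set to missing".

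**SAP, list and record of deviations.** Section 4.3 lists eight prohibited items. One is a live vaccine, up to three months after the last administration. Section 1 says: "Any methodological deviations from the protocol are documented".

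**The concern.** Treatment policy and a composite rule answer different questions. Under treatment policy, SALT30 (a 30% improvement in SALT) is the share of participants with that improvement whatever else they took. Under 5.7.2.2 it is the share with that improvement who have also not started a prohibited medication. A reader who takes the estimand from the protocol would misread the SAP's table. With no prespecified sensitivity analysis for binary endpoints, no planned summary that can be read would show how much of the rate comes from the rule.

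The trigger also deserves a look. Non-response after an agent that may regrow hair is a defensible choice, because the improvement cannot then be credited to IMG-007. That reasoning does not extend to a live vaccine, yet the word any includes it.

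**Working it through.** The visible text states no expected SALT30 rate, no rate of prohibited-medication use and no sample-size figures, so there is no plan figure to reproduce.

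**1. Strategies side by side**

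| Source | Event | Strategy |
|---|---|---|
| Protocol synopsis | All efficacy analysis | Treatment policy; details left to the SAP |
| SAP 5.7.2.2 | Treatment discontinuation | Treatment policy |
| SAP 5.7.2.2 | Any prohibited medication | Composite (non-responder) |
| SAP 5.7.3 | Other binary endpoints | Same as 5.7.2.2 |
| SAP 5.10.1, by cross-reference | Secondary endpoint after prohibited medication | Appears to be set to missing; 5.7.1 text not readable |

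The third and fourth rows do not match the first. The SAP contents list has no section on changes from the protocol, and the version history gives none.

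**2. The trigger list (SAP 4.3, eight items)**

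- Four refer to AA or hair regrowth in their own wording: topicals, oral or injectable agents for AA, phototherapy, and the final catch-all.
- Two are described as AA treatments in SAP 1.1: systemic immunosuppressants and oral JAK inhibitors.
- One, biologics, is linked to AA trials in Protocol 2.5.1.
- One, the live vaccine, has no stated link.

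Total: 4 + 2 + 1 + 1 = 8.

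**3. How long a live vaccine can trigger the rule**

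- The last dose is on Day 29, or Day 39 with the 10-day delay allowed in Protocol 6.5.
- Three calendar months is 89 to 92 days.
- Day 29: 29 + 89 = 118 to 29 + 92 = 121.
- Day 39: 39 + 89 = 128 to 39 + 92 = 131.
- The day count agrees with Protocol Table 5, where 29 + 84 = 113 and 29 + 140 = 169.

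The nine post-baseline SALT visits are Weeks 4, 6, 8, 12, 16, 20, 24, 30 and 36. The SAP 11.3 analysis window for Week 20 is Days 128 to 155. A vaccine by Day 121 therefore precedes every Week 20 value. After a delayed last dose, a vaccine as late as Day 131 could follow a SALT taken on Days 128 to 130 that still counts as Week 20. A Week 20 visit held on schedule (141 ± 3, so Day 138 at the earliest) comes after it. Normally, then, Week 20 and all later attended visits are recoded. A vaccine just after the Day 29 dose precedes eight visits, Weeks 6 to 36.

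**4. Size per recoded responder**, as 100/n with all n in the denominator

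- Cohort 1: 100/6 = 16.7 points
- Cohort 2: 100/24 = 4.2 points; two responders 8.3, three 12.5
- Pooled: 100/30 = 3.3 points

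Illustration, assuming 6 of 24 observed responders in Cohort 2. The 95% Clopper-Pearson limits are the 0.025 quantile of Beta(x, n−x+1) and the 0.975 quantile of Beta(x+1, n−x).

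| Recoded | Rate | 95% interval |
|---|---|---|
| 0 | 6/24 = 25.0% | 9.8 to 46.7 |
| 1 | 5/24 = 20.8% | 7.1 to 42.2 |
| 2 | 4/24 = 16.7% | 4.7 to 37.4 |

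**5. Expected size**, assuming a 25% response rate and use independent of response

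Expected loss = use × 0.25. Chance that at least one of 24 participants is a recoded responder = 1 − (1 − use × 0.25)^24.

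| Assumed use | Expected loss (points) | Chance of at least one |
|---|---|---|
| 1% | 0.25 | 5.8% |
| 5% | 1.25 | 26.1% |
| 10% | 2.5 | 45.5% |

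**The case against.** **The protocol delegates this to the SAP.** The sentence after the treatment-policy statement does so, and the statement stands only in the synopsis. One can read it as a default that the SAP then refines. This has weight, and it makes the remedy a reconciliation rather than a correction of an error. But leaving further detail to the SAP does not clearly permit a different strategy where the protocol says all.

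**The record may exist.** The estimand text of 5.7.1, and much of 7.1 and 7.2, cannot be read. A reader might infer that the departure is undocumented, or that percent change in SALT is also off treatment policy. Neither is established. Only the absence from readable text is, and the secondary-endpoint rule is known only through the pharmacodynamic section.

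**Observed data are already promised and listed.** The protocol says that efficacy analyses are in general based on observed data, though not whether that covers values after prohibited medication. SAP 5.3 plans a listing of prohibited medications with start dates, and 6.3 says that all measurements appear in listings. With about 30 participants, each recoded case could be traced. So the effect of the rule is not hidden; it is just not summarised.

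**The stakes are low.** The rule can only lower SALT30, SALT30 is exploratory, the primary objective is safety, and participants agree to avoid live vaccines in the relevant period (Protocol 5.2, criterion 18). All of this stands. An expected loss of 0.25 to 2.5 points is small beside an interval of 46.7 − 9.8 = 36.9 points.

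**The vaccine effect is not fixed.** A reader might infer that a vaccine always removes Weeks 20, 24, 30 and 36. The Week 20 analysis window allows an exception, and SAP 5.5 counts consent to the extended follow-up separately, so Weeks 30 and 36 need not apply to everyone.

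**Conclusion.** The point holds as a mismatch between two documents, with a modest consequence: minor to should-fix. For SALT30 and the other binary endpoints, the protocol names treatment policy and the SAP applies a composite rule after any prohibited medication. No readable SAP text names the difference, and no readable SAP summary gives the result that the protocol names. The live-vaccine trigger is a literal consequence of the wording and would be minor alone.

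The cost per recoded responder and visit is 16.7, 4.2 or 3.3 points for n = 6, 24 or 30. The total depends on use, which the documents do not give; the 25% response rate and the 1% to 10% range of use are assumptions. A reader might infer that the SALT30 result is seriously distorted. The documents do not support that: the rule is conservative, and its effect is small if use is rare.

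**What to change.** Before database lock:

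1. Add one prespecified SALT30-by-visit table under treatment policy, using all observed data, including data after prohibited medication. Do the same for percent change in SALT unless 5.7.1 already provides it.
2. Reconcile the protocol synopsis with SAP 5.7.2.2. State which estimand is the main one and record the reason. Either choice can be defended, and it is the sponsor's to make.
3. In 5.7.2.2, state that a live vaccine alone does not trigger non-response in the analysis and that observed data are used. SAP 5.10.1 already exempts two OX40 measures from its own rule, so an exception of this kind has a precedent. The list of prohibited treatments does not change.

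The cost is a few lines of SAP text and one or two tables from data already collected. The trigger stays somewhat blunt, since several listed items (topicals, phototherapy and the catch-all) rest partly on investigator opinion. The treatment-policy table shows how much the whole rule matters.
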